**4.1 Investigational product/treatment**

NA

**4.2 Use of co-intervention (if applicable)**

NA

**4.3 Escape medication (if applicable)**

NA

**5. INVESTIGATIONAL PRODUCT**

NA

**6. NON-INVESTIGATIONAL PRODUCT**

NA

## 7. METHODS

### 7.1 Study parameters/endpoints

#### 7.1.1 Main study parameter/endpoint

The primary outcome is a composite weighted score of functional status, postoperative surgical complications, re-admissions to hospital and major adverse cardiac events at three months after surgery and one year after surgery. Each event, complication or worsening in functional status are considered as a score of 1 to 3 points. These points are summed to calculate the total score. Table 2 gives an overview of the primary endpoint. Functional status will be assessed with two health domains of the Medical Outcome Study 36-item General Health Survey (RAND-36 version 2): physical functioning and physical health problems. These two scales and the other six scales are evaluated separately as secondary outcomes.

#### 7.1.1 Secondary study parameters/endpoints (if applicable)

The secondary endpoints are divided into seven domains: complications/ events, physical capacity, psychological health, -economic evaluation, lifestyle risk factors and potential mediators. In table 4 an overview is provided of the primary and secondary outcomes and the required amount of time to conduct the measurements.

##### *Complications and events*

The incidence of the parameters of the composite endpoint are analysed separately as secondary endpoint (Table 2). In addition, all-cause mortality will be defined in cardiac death and non-cardiac death. Table 3 shows the definitions of the other secondary complications and events.

##### *Physical health*

Cardiorespiratory fitness will be measured by the six minutes walking test (6MWT). This submaximal walking test mimics efforts in everyday life of patients with coronary artery disease, because most of the daily life activities are performed submaximally. In addition, a walking test is close to a real life situation, since walking is an important activity of daily living. A strong correlation ( $r = 0.82$ ,  $p < 0.001$ ) with VO2peak was shown by Tueller and colleagues (2010), however other studies found a modest correlation between the 6MWT and maximal oxygen uptake (VO2max, 0.6-0.7). From a meta-analysis strong evidence was found that the 6MWT was responsive to change in clinical status following cardiac rehabilitation. However, an increase in percentage between 2-8% should be taken into account, when the test is repeated. In addition, cardiorespiratory fitness is measured using results of the bicycle tests (oxygen uptake, heart rate and work load) which are performed in the context of the cardiac rehabilitation programs.

Muscle strength will be assessed with two hand dynameters. Grip strength will be bimanually measured with a JamarR Hydraulic Hand dynameter as measure for muscle strength of the upper extremities. Normative data of the grip strength test and 6MWT have been reported by Tveten and colleagues (2014).

For measuring isometric muscle strength (knee extension) the Q force is used. It consists of a chair with an attached, adjustable fixed leg brace at the front. It has three sensors, which are located in the brace to determine the generated force in Newton, the angle between the horizontal chair surface and the brace and the distance between the force transducer and the rotation axle of the brace in millimeter. Rails are attached at the left and

right bottom of the seat to which the brace is connected so that both the left and right leg can be tested (Figure 3).

Table 2: definitions of the composite weighted primary endpoint

Functional status	Score
Worsening in physical functioning (domain score of health related quality of life, rand36_v2)	1
No change or improvement in physical functioning	0
Worsening in physical problem (domain score of health related quality of life, rand36_v2)	1
No change or improvement in physical problem	0
An clinical relevant worsening is classified as minimal change according to Wyrwich et al., 2004 	
(Serious) Adverse Events	
No serious adverse event	0
Prolonged mechanical ventilation (Mechanical ventilation longer than 24 hours during initial postoperative ICU stay)	1
Lung infection (Positive sputum culture in the period between the surgery and when patient meets discharge criteria)	1
Delirium (In the period between the surgery and when patient meets discharge criteria: 1) A DOS score $\geq 3$ at hospital ward AND/OR 2) A positive ICU-CAM score (i.e. feature 1 plus 2 and either 3 or 4 present) at the intensive care by stay $> 1$ day AND/OR 3) Diagnosis confirmed by a psychiatrist, geriatrist or supervising specialist according to the DSM-IV criteria)	1
Re-admissions to intensive care unit (In the period between the surgery and when patient meets discharge criteria)	1
Deep wound infection (deeper tissues are affected (muscle, sternum and mediastinum) and must include: 1) surgical drainage / refixation OR 2) an organism is isolated from culture of mediastina tissue or fluid OR 3) antibiotic treatment, because of sternum wound) (up to 120 days)	2
Re-admissions to hospital (The number of an overnight hospital stay in the period between 30 days after surgery and one year after surgery)	1
Any cardiothoracic surgical interventions (graft- or valve failure, CABG, valve, aortic or other cardiac surgery  )	2
Any percutaneous interventions (PCI, TAVI, etc.)	1
Myocardial infarction (According to the third universal definition of myocardial infarction  )	2
Cerebral vascular accident (CVA)/stroke (Acute neurological event of at least 24 hours of duration, with focal signs and symptoms and without evidence supporting any alternative explanation. Diagnosis of stroke requires confirmation by CT or MRI or pathological confirmation.)	2
Death (all-cause mortality)	3
Total score = sum of physical status en serious adverse events	

According to the definitions of the 'Begeleidingscommissie Hartinterventies Nederland'; Thygesen et al., 2012; ICU: Intensive care unit; CABG: coronary arterial bypass graft; PCI: percutaneous coronary intervention; TAVI: transcatheter aortic valve implantation

Table 3: definitions of the secondary complications and events

Parameter	Definition
Atrial fibrillation	New onset of atrial fibrillation requiring medical treatment or cardioversion in the period between the surgery and when patient meets discharge criteria**
PICU	An ICU stay larger than 24 hours
Re-thoracotomy for bleeding/tamponade	Surgical incision into the sternum as a result of a bleeding or tamponade ( up to 120 days after surgery ) a) acute: presented within 24 hours after surgery b) late: presented after 24 hours after surgery
Re-thoracotomy dehiscence	Aseptic wound dehiscence ( up to 120 days after surgery )
All cause re-admissions to hospital	The number of overnight hospital stays in the period between 30 days after surgery and one year after surgery for any reason
Cardiac re-admissions to hospital	The number of overnight hospital stays in the period between 30 days after surgery and one year after surgery with a directly related cardiac cause
All cause hospitalization days	Total number of days of hospitalization in the period between 30 days after surgery and one year after surgery for any reason
Cardiac hospitalization days	Total number of days of hospitalization in the period between 30 days after surgery and one year after surgery with a directly related cardiac cause
Cardiac death	Any death due to proximate cardiac cause (e.g. Myocardial infarct, low-output failure, fatal arrhythmia), unwitnessed death and death of unknown cause, and all procedure related deaths, including those related to concomitant treatment*
Non-cardiac death	All death with a non-cardiac cause

PICU: prolonged stay at the intensive care unit; \*specifically, any unexpected death even in patients with coexisting potentially fatal non-cardiac disease (e.g. cancer, infection) will be classified as cardiac death; \*\*A spontaneous transient period of atrial fibrillation, without any consequences for the patient is not mentioned as an event.

Functional muscle strength of the lower extremities will be assessed by the 'ten times sit to stand' test (STS). This test measures mainly muscle strength of the lower extremities and shows a correlation 0.5-0.6 with a combined score of specific lower limb strength measures (i.e. strength of a hip extension during a leg press, knee extension, and ankle plantar flexion, Jones et al., 1999). The modest correlation is possibly because performance on the STS test may also be influenced by other components like balance and reaction time. The STS has a high test-retest reliability in patients enrolled in cardiac rehabilitation (ICC = 0.87).

The Katz Index of Independence in Activities of Daily Living assesses functional status as a measurement of the client's ability to perform activities of daily living independently. The Index ranks adequacy of performance in the six functions of bathing, dressing, toileting, transferring, continence, and feeding. The scoring system has a range of 0 to 6 points, and a higher score indicates more dependency in performing daily

functioning. The Katz is validated by Reijneveld and colleagues (2007). This questionnaire is also included in the routine preoperative assessment.

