### *Randomization*

Patients are randomized to two groups. One group will start a regular phase II CR program after surgery and are considered as the POST group. The other group will be randomized to a combined pre-and postoperative rehabilitation program (the PRE+POST CR program). The latter group is considered as the PRE+POST group. The PRE+POST group follows the CR program in the UMCG, location Beatrixoord. The POST group will receive the CR in the referred hospital. All hospitals provide a basic postoperative outpatient CR program, which is generally accepted care in the Dutch health care system. These CR programs are based on the multidisciplinary guidelines cardiac rehabilitation 2011 of the association of Dutch Cardiac Rehabilitation. The inclusion period is estimated to last 3.5 years, based on the power analyses (Section 3.4). The total study duration will therefore be 8.5 years (including follow-up of mortality up to five years). Patients are treated according to the intention to treat principles.

[figure not shown]

Figure 2: Research design of the randomized controlled trial. The phases of the CR programs and times of measurement are shown relative to the moment of surgery. T1 and T2 are preoperative measurements, T3, T4, T5 and T6 are postoperative and follow up measurements. Mortality is screened up to 5 years after surgery. H= hospital stay; OR = operation.

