#### 3.4 Sample size calculation

The composite weighted score consists of a summary score for worsening in functional status and the number of postoperative surgical complications, readmissions to the hospital and major adverse cardiac events (Table 2). The primary endpoint is partly adapted from the A-HeFT study.

The mean weighted score is estimated on 1.0 with a standard deviation of 0.9. This estimation is based on historical data of the UMCG (postoperative surgical complications and mortality), the Fitness Study - an on-going pilot study in the UMCG among the same population - (functional status), two literature studies: Iribarne et al., 2014 (hospital readmissions) and Serruys et al., 2008 (stroke and percutaneous interventions) and Meetbaar Beter database (re-interventions and myocardial infarction). A decrease of 0.3 means on average a decrease of one complication/event or worsening in functional status in 30% (or 10-20% decrease in major cardiac events or death) of the patients, which is considered to be clinically relevant. A group of 286 patients (143 in the PRE+POST group

and 143 in the POST group) achieve 80% power to detect a difference in the weighted score of 0.3, when alpha is set on 0.05.

The number of eligible patients is estimated to be 170 per year. We expect that 100 patients (60%) per year will be enrolled in the study. Therefore the estimated inclusion period is 3.5 years (n=350). In the total sample size (n = 350) a withdrawal of ±20% is incorporated. Because the mean score is estimated on different sources, different interim analyses are performed (section 7.4). Based on the interim analyses, the sample size can be adapted to ensure power.

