
Surgery and hospitalization
 
- Admission to hospital, one day before surgery
 
- Hospitalization till UMCG discharge criteria are met.
 
(possible transfer to other hospital after four to seven days)
	
Surgery and hospitalization
 
- Admission to hospital, one day before surgery
 
- Hospitalization till UMCG discharge criteria are met.
 
- Transfer to rehabilitation center when discharge criteria are met

Postoperative cardiac rehabilitation program (POST group)	Pre- and postoperative cardiac rehabilitation program (PRE+POST group)

Week 2-4 after surgery: -
 
 
- Further recovery at home (no support)
 
	
Week 2-4 after surgery: POST-in phase
 
 
- 15 to 18 days clinical cardiac rehabilitation period
 
 
Physical therapy
 
 
- Individual sessions (twice a day)
 
 
When exercise tolerance of patient is acceptable:
 
 
- IMT (1x p/wk under supervision, 2x p/wk on their own, 6 cycles of six repetitions, up to 80% of maximum inspiratory pressure)*
 
- Aerobic cycle ergometry (daily, up to 25 min**, RPE 3)
 
- Resistance training (daily, and cardiofitness (3x p/wk, 10 min, moderate intensity (RPE of 3 on a Borgscale 0-10)
 
- Weekly, a 30 min session of body awareness
 
 
Dietary advice and psychological counseling
 
 
- Group education about handling with the heart surgery and strategies to prevent re-intervention or cardiac events
 
- Individual session with the psychologist and dietician and psychological sessions in the first week after surgery
 
- Individual sessions with psychologist/dietician on indication
 
 
Smoking and labor consultation on indication

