***Procedure of primary outcome***

Postoperative complications are routinely collected in standard care. These parameters will therefore be derived from medical record and hospital database. At T4 and T6 (3-4 months and one year follow up) patients are asked if they were hospitalized, underwent any cardiothoracic surgical intervention or any percutaneous interventions since the surgery. In addition, they will be asked if they had a myocardial infarction or CVA. The researcher will check documentation at the hospital in which the intervention or treatment was performed, if

patients have had one of these major adverse cardiac events. The rate of mortality will be checked in the municipal administration. The cause of death is reviewed by interrogation of the general practitioner, if patient has died outside of the hospital.

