#### *Potential mediators*

The summary score of the different dimensions of illness representations (IPQ-R) and self-efficacy (CSA) are calculated and handled as continuous variable.

Mean and standard deviation are calculated for continuous variables. Multivariate analyses (inclusive multilevel analyses) are performed to determine time\*group differences for the continuous variables. Non-parametric tests are used if distributions are non-normal. In addition, descriptive statistics will be presented in median and (IQ) range. In all statistical analyses, a two-sided  $p<0.05$  is considered statistically significant.

Missing data analysis will be performed, meaning that the amount and nature of missing data will be studied and depending on this, adequate strategies to handle missing data will be applied (e.g. multilevel analyses). Patients are treated according to the intention to treat principles.

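### Deep wound infection, worth 2 points to day 120, has no capture route of its own after discharge, and allocation may affect how completely it is recorded

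*Combined protocol and SAP*

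**What the plan says.** **Definition.** Table 2 in Section 7.1.1 scores deep wound infection 2 points. Deeper tissue (muscle, sternum, mediastinum) must be affected, and one of three criteria must be met: surgical drainage or refixation, a positive culture, or "antibiotic treatment, because of sternum wound) (up to 120 days". Section 2 (Screening outcomes) repeats the 120-day window.

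**Sources.** Section 7.3 (Procedure of primary outcome) says of postoperative complications: "These parameters will therefore be derived from medical record and hospital database". At T4 and T6 patients are asked about hospitalisation and about surgical or percutaneous intervention, and then: "In addition, they will be asked if they had a myocardial infarction or CVA". Documentation at the treating hospital is checked for patients who had one of the major adverse cardiac events. General practitioners are contacted only about cause of death.

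**Setting after surgery.** PRE+POST patients spend 15 to 18 days as inpatients at the UMCG rehabilitation location and then have four weeks of outpatient sessions (Section 2, Randomization; Section 4, Table 1). For POST patients, Table 1 gives weeks 2 to 4 as "Further recovery at home (no support", and Section 2 adds: "The POST group will receive the CR in the referred hospital".

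**The concern.** Set Table 2 against the ways its events are found. Prolonged ventilation, lung infection, delirium and ICU readmission belong to the index stay. Readmission, surgical and percutaneous intervention, myocardial infarction and CVA are each prompted by a named question at T4 and T6. Death is checked in the municipal administration. Deep wound infection can occur or be treated well after discharge, yet it is left to routine records, with no named question and no stated retrieval from an outside provider.

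That would matter less if gaps in the record were equally likely in both arms. Here the randomised programme itself determines who sees the wound and where treatment is written down. A case seen during inpatient rehabilitation at the UMCG location is likely to be on file. The same case treated by a general practitioner or another hospital may not be. If so, PRE+POST would score more points for the same true rate, and a real benefit would be diluted. The blinded endpoint committee does not cure this: it judges the cases put before it, and nothing in the plan says it searches for unrecorded ones. Section 9.2 also compares each component by chi-square test, and there a detection gap is not diluted by the other components.

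**Working it through.** **Inputs from the documents.** Section 3.4: "The mean weighted score is estimated on 1.0 with a standard deviation of 0.9"; 143 patients per arm "achieve 80% power to detect a difference in the weighted score of 0.3, when alpha is set on 0.05". Section 9.2: "a two-sided $p<0.05$ is considered statistically significant". Table 2: weight 2.

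**Inputs that are assumptions.** True deep-infection rate r, equal in both arms, and share u of cases missed in POST only. The documents give neither. The figure of about 18% in Section 1 is for infections in general and cannot stand in for r.

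**1. The plan's own figure.** n per arm = 2(z₀.₉₇₅ + z₀.₈₀)² SD²/δ² = 2 × (1.960 + 0.842)² × 0.81/0.09 ≈ 141.3, so 142. The t-test version gives 142.2, so 143. Power at 143 per arm is 0.805 (normal) or 0.802 (t). The stated sample size reproduces.

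**2. Shift per missed case.** Bias = 2 × r × u. Each 1% of patients missed only in POST gives 2 × 0.01 = 0.02 points, and 0.02/0.3 = 6.7% of the target difference.

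**3. Illustrative range.** SE = 0.9 × √(2/143) = 0.106. Power = Φ((0.3 − bias)/SE − 1.960), with SD held at 0.9 and u = 50%.

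| Assumed r | Bias (points) | Share of 0.3 | Power at 143 per arm | n per arm for 80% |
|---|---|---|---|---|
| 1% | 0.01 | 3.3% | 0.78 | 152 |
| 2% | 0.02 | 6.7% | 0.75 | 163 |
| 3% | 0.03 | 10.0% | 0.72 | 175 |
| 5% | 0.05 | 16.7% | 0.65 | 204 |

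In cases, this is 143 × 0.01 × 0.5 = 0.7 to 143 × 0.05 × 0.5 = 3.6 infections missing from the POST count.

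**4. Could it look like harm?** With no true difference, the two-sided rejection probability rises from 0.050 to between 0.051 (r = 1%) and 0.076 (r = 5%). The largest bias in the table, 0.05, is 0.05/0.106 = 0.47 of a standard error.

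**5. When the arms differ in observation.** In weeks 2 to 4, PRE+POST patients are inpatients and POST patients are at home. After that both arms attend outpatient sessions. PRE+POST starts at about week 5 and runs four weeks, so ends at about week 9. POST starts at about week 3 to 6 and can be prolonged to 16 weeks. The 120 days are about 17 weeks (120/7).

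**6. Does T4 close the window?** T4 falls at 3 to 4 months. At 3 × 30 = 90 days it leaves about 30 days of the window open, so a question asked only at T4 can miss late cases.

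**The case against.** The best defence is that the plan does question patients, in both arms. Section 7.3 says at T4 and again at T6 that questions on the primary endpoint are put to the patient, and deep wound infection is a primary-endpoint item. Section 8.2.2 has adverse events asked at T2, T3, T4 and T6. The hospitalisation question should prompt infections treated in hospital, and the MCQ records health-care use. A reader might infer that patients are never asked about wound problems; these provisions rule that reading out. What remains is narrower. Where the primary-endpoint questions are itemised, wound infection is absent. No text links adverse-event or MCQ answers to Table 2 scoring. The document check is worded for cardiac events, although that clause is loose and could be meant to cover every listed event.

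Three other strong readings also fail.

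- A reader might infer that any antibiotic course for the chest wound scores 2 points. Table 2 requires deeper tissue to be affected first, so treatment of a superficial wound does not count.
- A reader might infer that detection is shown to be higher in PRE+POST, over nearly the whole 120 days. The documents do not say so. The source records are not expressly limited to the UMCG, Section 4 describes an outpatient programme at the UMCG itself, and the clear contrast is confined to weeks 2 to 4.
- A reader might infer a large bias, such as a detection gap of 5 or 10 percentage points. With half of cases missed in POST, those gaps need true rates of 10% and 20%. The latter exceeds the roughly 18% that Section 1 gives for infections in general. Nothing in the documents supports either.

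**Conclusion.** The gap in the capture procedure is in the text: a 2-point item with a 120-day window has neither a named question nor a stated route to outside records. Unequal capture by arm is a plausible consequence of the two care pathways, not an established one. If it occurs, it raises the PRE+POST score relative to POST and dilutes a benefit; the illustrated sizes give little ground for expecting a false signal of harm.

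The size cannot be fixed from the documents. The firm figure is 0.02 points per 1% of patients missed only in POST. The range of 0.01 to 0.05 points, with power of 0.78 to 0.65 against a planned 0.80, rests on assumed true rates of 1-5%, half of cases missed in POST, none missed in PRE+POST, and an unchanged SD. With equal ascertainment the bias is zero and the sample size stands. This is an inexpensive improvement worth making before follow-up data accrue, because unrecorded events may be hard to recover later. It is not a flaw that invalidates the design.

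**What to change.** In Section 7.3 (Procedure of primary outcome):

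- Add a question for all patients at T4, repeated at T6 to complete the window to day 120: since the operation, has there been a sternal wound infection, wound surgery, or antibiotics for the chest wound, from any provider? Ask for dates, so that only events up to day 120 are scored.
- For every positive answer, retrieve the record of the treating hospital or general practitioner, by the same procedure in both arms.
- Send these cases to the blinded endpoint committee for scoring against the existing Table 2 definition, which need not change.

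The cost is one extra question at two existing visits and some record requests. Clinical care is unaffected.

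A sensitivity analysis counting only cases with drainage, refixation or positive deep culture is optional. It does not replace equal ascertainment, because drainage or culture at an outside hospital faces the same retrieval gap.
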